#### 6.3.2.4 IVIg history

IVIg history will be summarized for the SAF set.

Time between historical first schedule of IVIg administration and screening will be derived as follows:  
Date of screening visit – start date of the first IVIg administration of IVIg +1

The start date of the first IVIg administration:

- if day and month are missing, 01-Jul will be imputed
- if day is missing, 15 will be imputed.

Time between first schedule of IVIg administration and screening will be summarized. For IVIg administration ongoing at screening, IVIg duration and dose and frequency will be summarized. IVIg frequency will be presented by stratification factor issued from the IWRS and eCRF if they differ.

IVIg duration ongoing at screening will be derived as follows:

screening date – starting date of last IVIg administration stable before screening \*+ 1

\* last IVIg administration stable before screening is defined as: for the IVIg administration ongoing at screening (ongoing = YES in IVIg history page with non-missing IVIg dose frequency), the oldest administration with same frequency and dose, independently of the treatment name.

The starting date of last IVIg administration stable before screening:

- if day and month are missing, 01-Jul will be imputed
- if day is missing, 15 will be imputed.

IVIg history will be summarized in a listing.

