#### 6.2.7.2 Prior and concomitant medications missing dates

Medications and procedures administered will be classified by period of use as prior, concomitant or both prior and concomitant to IMP therapy. In the event of partial dates, the available date information will be used to categorize the initiation period accordingly. In the event that the classification is ambiguous, including for cases of completely missing dates, the medication will be assumed to be both prior and concomitant unless indicated as prior only due to the given stop date.

The following date imputation rules for partially missing dates reflect the above convention:

1. End date: Missing day will be imputed as the last day of the month, and missing month will be imputed by December, if not resulting in a date later than the date of the participant's death, date of study discontinuation or date of study completion. In the latter case, the date of death/date of study discontinuation/ date of study completion will be used to impute the incomplete end date.
2. Start date: Missing day will be imputed as the first day of the month, and missing month will be imputed by January.
3. If the start date is completely missing, then:
  - a. If the end date is prior to the date of first administration of the IMP, then the medication is considered as prior
  - b. If the end date is prior to the date of last administration of the IMP, then the medication is considered as prior and concomitant
  - c. If the end date is completely missing or after the date of last administration of the IMP, then the medication is considered as prior and concomitant.

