#### 6.3.2.3 MMN disease history and MMN diagnosis

MMN disease history will be summarized for the SAF set.

Estimated duration of the disease since diagnosis at randomization will be derived as follows:

Estimated duration of disease since diagnosis = (Date of randomization – date of diagnosis +1)/365.25.

For the date of diagnosis:

- if day and month are missing, 01-Jul will be imputed
- if day is missing, 15 will be imputed.

Estimated duration of the disease since diagnosis at randomization, the most affected hand and the 2 most important muscles groups affected by MMN will be reported.

For the estimated duration of the disease since diagnosis at randomization in the summary table, results will be rounded in year with no decimal places for min and max, one decimal place for mean median and 2 decimal places for SD.

A tabulation will summarize the confirmation of diagnosis and IVIg dependency at screening and IMV1 in the SAF set.

MMN history will be reported in a listing. Confirmation of diagnosis and IVIg dependency by MCC will be listed.

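### Year-only IVIg start dates are imputed to 1 July with no upper bound, so a regimen begun in the screening year can be given a zero or negative duration

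*SAP*

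**What the plan says.** SAP 6.3.2.4 (IVIg history) defines two durations in days:

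- Time since the first IVIg schedule: "Date of screening visit – start date of the first IVIg administration of IVIg +1".
- Duration of the regimen ongoing at screening: "screening date – starting date of last IVIg administration stable before screening", again with 1 added.

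The regimen in the second is found by looking back, "for the IVIg administration ongoing at screening (ongoing = YES in IVIg history page with non-missing IVIg dose frequency", to the oldest administration at the same dose and frequency.

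Both start dates carry the same rule for partial dates: "if day and month are missing, 01-Jul will be imputed", and "if day is missing, 15 will be imputed". Neither is limited by the screening date.

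Section 6.3.2.3 uses the same two imputations for the date of diagnosis, with randomisation as the reference: "Estimated duration of disease since diagnosis = (Date of randomization – date of diagnosis +1)/365.25".

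Sections 5.2 and 6.2.7 contain no general rule that bounds these dates. Section 6.2.7 does bound some others. In 6.2.7.2, for example, an imputed medication end date stands only "if not resulting in a date later than the date of the" participant's death, discontinuation or completion.

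**The concern.** A regimen that is ongoing at screening cannot have started after screening, and neither can the first IVIg administration. With the added day, the smallest legitimate duration is 1 day. A mid-year imputation with no upper bound can break that limit whenever the known year is the screening year. This is a stated rule that returns an impossible value, so it goes beyond a missing detail.

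What is at stake is the description of prior treatment. The objectives concern participants previously stabilised with IVIg, and the IVIg history table (14.1.12) is planned for both interim analyses and the final analysis. In a small group, one impossible value becomes the reported minimum and pulls the mean down. Without a written rule, the programmer must either leave the value in or improvise a correction.

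**Working it through.** The SAP states no figure to reproduce, so the check applies its formula to calendar dates. A non-leap year is used; a leap year adds one day to the extremes.

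**Inputs.** Duration = screening date - start date + 1 (6.3.2.4). Imputed start = 01-Jul of the known year. Shortest IVIg interval 2 weeks and shortest IVMP 35 days (2.1). Cohort size 24, randomised 2:1 (2.2), so placebo per cohort = 24/3 = 8.

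**Year only known, equal to the screening year.** 01-Jul is day 182 of the year.

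- Screening 01-Jan: 1 - 182 + 1 = -180 days.
- Screening 15-Mar (day 74): 74 - 182 + 1 = -107 days.
- Screening 30-Jun (day 181): 181 - 182 + 1 = 0 days.
- Screening 01-Jul: 182 - 182 + 1 = 1 day, so the problem ends here.

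The non-positive dates are 01-Jan to 30-Jun, which is 181 of 365 calendar days.

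**Effect on a mean.** The error is the imputed start minus the true start. The true start cannot be before 01-Jan of the known year, so the error is at most 182 - 1 = 181 days. In a group of 8 that is 181/8 = 22.6 days. For screening on 15-Mar, the true duration lies between 1 and 74 days. The error is therefore 108 to 181 days, and the mean shifts by 108/8 = 13.5 to 22.6 days.

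**Day missing, start month equal to the screening month.** Screening on days 1 to 14 gives 1 - 15 + 1 = -13 up to 14 - 15 + 1 = 0. The regimen would then have started at most 14 - 1 = 13 days before screening, which is less than one 2-week interval.

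**Diagnosis.** With a year-only diagnosis in the randomisation year, randomisation before 01-Jul gives 0 or less. If diagnosis precedes the 35-day IVMP, the earliest such randomisation is 05-Feb (day 36): 36 - 182 + 1 = -145 days, or -145/365.25 = -0.40 years. The day-15 route would need a diagnosis in the month of randomisation, hence within the IVMP.

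**With the midpoint rule.** For screening on 15-Mar and only the year known, the midpoint of 01-Jan and 15-Mar, rounded down, is 06-Feb (day 37). The duration is 74 - 37 + 1 = 38 days, within the possible 1 to 74. For screening on 01-Jan the midpoint is 01-Jan and the duration is 1 day.

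**The case against.** The strongest reply is that the case may never arise. It needs a recent regimen whose month of start is unknown, although its dose and frequency come from the medical record. The protocol is not at hand, and an entry requirement for stable IVIg could make such records rare. This stands in part: the frequency is unknown. A same-year start with screening before July would, however, stay possible unless the requirement were about six months. If just one 14-day interval must have elapsed, the earliest screening is 15-Jan and the extreme becomes 15 - 182 + 1 = -166 days.

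Several stronger readings are tempting and not supported:

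- **That half of such records go wrong.** 181/365 only counts calendar days. If start and screening were both uniform over the year, with start not after screening (an assumption), the share would be about 25%: (181 x 182)/(365 x 366) = 0.247.
- **That a shift of 22 days is typical or a minimum.** It is the ceiling for one value in a group of 8.
- **That the SAP breaks its own convention.** Its explicit caps are on end dates. The medication start rule in 6.2.7.2 has no cap, but it imputes the earliest possible date and so cannot overshoot in this way. The comparison shows that bounding is familiar to the authors; it does not show a contradiction.
- **That evidence of IVIg dependency is undermined.** Dependency is assessed by the MMN Confirmation Committee, and baseline is established over three IVIg cycles. Neither is stated to use this derived duration.
- **That disease duration is materially at risk.** Its minimum and maximum are shown without decimals, so -0.40 years would print as zero.

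**Conclusion.** The concern holds as a narrow defect. For start dates with only the year known in 6.3.2.4, the rule gives 0 to -180 days when the year is the screening year and screening falls from 01-Jan to 30-Jun. The same imputation in 6.3.2.3 can in principle do this for diagnosis, but that is unlikely. The day-15 rule can be set aside in practice in both sections.

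The reach is limited to the descriptive IVIg and MMN history tables (14.1.12 and 14.1.10) and their listings. No endpoint, analysis set or model shown in the SAP uses these durations. The conclusion rests on the literal formula and on a start date that cannot follow screening. The number of affected participants is unknown, and zero is possible. Severity: nice to have.

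**What to change.** Add to 6.3.2.3 and 6.3.2.4: *If the imputed date is later than the screening date, impute the midpoint between the first day of the known year (or month) and the screening date, rounded down to a whole day.*

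The imputed date then stays within its known bounds. A record whose imputed date is on or before screening does not change. The midpoint is preferable to a simple cap. Setting the date to screening gives every affected participant a duration of 1 day, and the day before screening gives 2 days; both are implausible for a stable regimen. The day before screening can also fall outside the known year or month.

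The cost is one sentence in each of two sections and a short programming change. No data collection or endpoint derivation is touched.

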### 6.3.2.5 IVIg treatment during IVMP

For each participant, the average IVIg dose interval in weeks will be calculated as:

*Average IVIg dose interval (weeks) = [(Starting date of the last IVIg administration during IVMP – starting date of the first IVIg treatment during IVMP) / (Number of IVIg administrations during IVMP - 1)] / 7*

Total IVIg dose (g/kg), average IVIg dose per week (g/kg) and average IVIg dose interval (week) will be summarized by treatment group and overall and by IVIg dose frequency subgroup using descriptive statistics during the IVMP on the SAF set.

During IVMP, for the total number of IVIg administrations, in case of unscheduled visits with IVIg administrations :

- If unscheduled visits are not on consecutive days, one unique IVIg administration should be counted per unscheduled visits
- If unscheduled visits are performed on consecutive days, then IVIg administrations performed on these consecutive day should be counted as a single administration.

In case of IVIg administrations given on several days for a single visit, a unique record (e.g. first day) should be considered to determine the dose of IVIg administered at this visit. The total IVIg dose over the IVMP period is the sum of the unique doses associated to each visit, including unscheduled visits.

All visits (scheduled, unscheduled) during IVMP will be taken into account.

IVIg administrations during IVDP and IVMP will be listed.

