*Time to relapse = (date of first clinical deterioration during DBTP – date of randomization) + 1*

The data of participants who do not meet criteria for clinical deterioration will be censored. The censoring date will be determined as follows:

- If the participant completes DBTP, the censoring date will be the date of last visit V14 (D113)
- If the participant early discontinues treatment during DBTP, without clinical deterioration, the censoring date will be the date of early discontinuation of treatment
- If the participant is ongoing in cohort 2, the censoring date will be the date of the data cutoff date

Participants who are lost to follow-up in the DBTP will be censored at the date of last visit available.

The statistical analysis will be similar to the survival analysis described above for time to first retreatment with IVIg.

Time to relapse data will be listed.

- Number of participants retreated with IVIg

The number and percentage of participants retreated with IVIg during the DBTP will be summarized by treatment. Categories will be presented as follows:

- Not retreated
- Retreated once
- Retreated twice
- Retreated more than twice
- Total number of IVIg administrations

In addition, a cross tabulation will display the status of IVIg retreatment (Yes/ No) according to the following worsening status:

- clinical deterioration [REDACTED]
- [REDACTED]
- [REDACTED]
- [REDACTED]
- [REDACTED]
- [REDACTED]

An additional table with each worsening status combined with the IVIg retreated status (IVIg retreated / Not retreated with IVIg) will be summarized as well.

- IVIg administrations during DBTP

The following endpoints will be described for participants retreated with IVIg: Number of IVIg administrations during DBTP, Total IVIg dose (g/kg), Average IVIg dose / week (g/kg) and Average IVIg dose interval (weeks)

During the DBTP, IVIg administrations reported on several visits and linked to the same visit number should be counted as a single administration. In case of IVIg administrations performed on several days for unscheduled visits, and within maximum 5 days apart from the first one to the latest one, then it should be counted as a single administration. The total number of IVIg retreatments is the sum of single IVIg administrations during DBTP. The total IVIg dose over the treatment period is the sum of doses over all single IVIg administrations.

- Number of IVIg administrations during DBTP

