The number of IVIg retreatments during the DBTP will be presented.

- Total IVIg dose (g/kg)

The total IVIg dose (g/kg) during the DBTP will be presented by IVIg dose frequency subgroup.

- Average IVIg dose / week (g/kg)

The average IVIg dose per week (g/kg) during the DBTP will be presented by IVIg dose frequency subgroup.

*Average IVIg dose per week (g/kg) = Total IVIg dose / [(End DBTP date – starting date of the first IVIg retreatment+1)/7]*

- Average IVIg dose interval (weeks)

For each participant, the IVIg interval in weeks between 2 retreatments will be calculated as:

*Average IVIg dose interval (weeks) = [(Starting date of the nth IVIg retreatment – starting date of the first IVIg retreatment) / (Number of IVIg administration during DBTP-1)] / 7*

The average IVIg dose interval in weeks for participants retreated at least twice during the DBTP will be presented by IVIg dose frequency subgroup.

The number of IVIg administrations during DBTP, the total IVIg dose, the average IVIg dose pr week and the average IVIg dose interval will be listed.

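### In the IVMP, IVIg courses recorded as consecutive unscheduled visits are merged for the count but not for the dose, and the count follows a different merging rule from the DBTP

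*SAP*

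**What the plan says.** **IVMP (SAP 6.3.2.5).** The counting rule opens with its scope: "During IVMP, for the total number of IVIg administrations, in case of unscheduled visits with IVIg administrations". Two cases follow. For non-consecutive days, "If unscheduled visits are not on consecutive days, one unique IVIg administration should be counted per unscheduled visits". For consecutive days, "then IVIg administrations performed on these consecutive day should be counted as a single administration".

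Dose has its own paragraph. Where one visit spans several days, a single record, for example the first day's, supplies that visit's dose. Then: "The total IVIg dose over the IVMP period is the sum of the unique doses associated to each visit, including unscheduled visits". The merged administration does not appear in the dose rule.

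The average dose interval is the time from first to last start date, divided by "Number of IVIg administrations during IVMP - 1)] / 7".

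**DBTP (SAP 6.5.1.1).** Infusions recorded on several visits and "linked to the same visit number should be counted as a single administration". Unscheduled infusions on several days are merged if "within maximum 5 days apart from the first one to the latest one, then it should be counted as a single administration"; they need not be consecutive. Total dose is then summed over these merged administrations. The average dose interval has the same form, with divisor "Number of IVIg administration during DBTP-1)] / 7".

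The IVMP results go into Table 14.1.13 and the DBTP results into Table 14.2.1.5. The current SAP text gives no reason for the difference and nothing that reconciles the two rules.

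**The concern.** There are two separate issues.

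**Dose within the IVMP.** The count and the dose use different units. The count uses the merged administration and the dose uses the visit. A course recorded as two unscheduled visits on consecutive days is therefore one administration with two doses. Whether that inflates the total depends on what a dose record holds. The section's one-record rule for multi-day visits makes sense only if each record carries the course dose, and under that convention the course is counted twice.

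**Count across periods.** Unscheduled visits recorded separately, on non-consecutive days at most 5 days apart, are separate administrations in the IVMP and one administration in the DBTP. The interval formulas look identical but their divisors are built differently.

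At stake are the IVMP total dose, dose per week and dose interval in Table 14.1.13, overall and by IVIg frequency subgroup. Unscheduled IVIg before randomization is a real situation. Section 6.5.1.1 allows for it when it defines time to first retreatment. The modification history also records that the IVMP count with unscheduled visits was handled incorrectly at interim analysis 1.

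**Working it through.** The plan gives no figure to reproduce. The check applies both rules to one constructed participant.

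**Inputs**
- Four-weekly schedule, IVMP days 1, 29 and 57 (SAP Table 2). The span is 57 − 1 = 56 days.
- One unscheduled course on two days, recorded as two separate unscheduled visits. The days are assumed: 43 and 44, or 43 and 45.
- Interval in weeks = (last start − first start) / (N − 1) / 7.
- Course dose D, assumed equal for all courses.
- 16 participants per arm (SAP 6.1). One affected participant per arm is assumed.

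**Dose, unscheduled days 43 and 44**
- The count is 3 + 1 = 4 administrations under both rules.
- If each record holds the course dose, the sum per visit is 3D + D + D = 5D. The sum per merged administration is 4D. The total as written is 25% too high for this participant.
- If each record holds that day's dose, the unscheduled part is D/2 + D/2 = D and its sum is right. The one-record rule then understates any visit given over several days.
- Dose per week is proportional to total dose, so it carries the same ratio as long as its time divisor is unchanged.
- Arm of 16, the other 15 at 3D, course-dose records: (15 × 3D + 5D)/16 = 3.125D against (15 × 3D + 4D)/16 = 3.0625D. The ratio is 50/49, about 2% higher.

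**Count and interval**

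| Unscheduled days | IVMP rule | DBTP rule |
|---|---|---|
| 43 and 44 | N = 4; 56/3/7 = 2.67 weeks | N = 4; 2.67 weeks |
| 43 and 45 | N = 5; 56/4/7 = 2.00 weeks | N = 4; 56/3/7 = 2.67 weeks |

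For days 43 and 45 the ratio is (1/4)/(1/3) = 3/4, so the interval is 25% shorter under the IVMP rule. The span cancels, so this ratio holds at every dosing frequency with three scheduled infusions and one such course.

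**Arm level, days 43 and 45, the other 15 participants at 4.00 weeks**
- IVMP rule: (15 × 4.00 + 2.00)/16 = 3.875 weeks.
- DBTP rule: (15 × 4.00 + 2.667)/16 = 3.917 weeks.
- The difference is 0.042 weeks, or 1.1%. The minimum is 2.00 against 2.67. The median and quartiles stay at 4.00.
- In an assumed frequency subgroup of 4 with one such participant: (3 × 4.00 + 2.00)/4 = 3.50 against (3 × 4.00 + 2.667)/4 = 3.67 weeks, or 4.5%.

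**The case against.** **The trigger is narrow.** The IVMP rule counts by visit, not by day. A multi-day unscheduled course entered under one visit is one administration with one dose, rest day or not. The count divergence needs visits recorded separately, on non-consecutive days, within 5 days. This stands, and the point is limited to that case.

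**Different rules are not wrong in themselves.** IVMP infusions follow an established regimen within visit windows, so unscheduled IVIg is the exception. In the DBTP the first retreatment takes place at an unscheduled visit, which gives a broader merge more to do there. No visible analysis compares the two intervals. The DBTP interval covers only participants retreated at least twice, whereas the IVMP interval is summarized on the safety set. This also stands. A common counting rule would remove one source of difference but would not make the two statistics fully comparable.

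**The dose rule may simply be silent.** One could read merged visits as a single visit for dose too. The text does not say so: the merge is tied to the count, and the dose sentence names visits and expressly includes unscheduled ones. It is also true that the sum is right if each record holds one day's dose. That reading, however, undermines the one-record rule in the same paragraph.

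**A reader might infer more.** The 25% figures could be taken as the error in the table, or the point as a bias in efficacy. Neither is supported. The 25% belongs to one constructed participant. The IVMP precedes randomization, and time to first retreatment, retreated yes or no, and the between-arm comparisons do not use these derivations.

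**Conclusion.** The point holds as a minor inconsistency in a descriptive derivation.

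The dose part is the firmer one. As written, section 6.3.2.5 counts a course on consecutive unscheduled visits once and sums its dose twice. This rests on the record holding the course dose, which the section's own one-record rule implies, and on that convention applying to separate unscheduled visits as well. The SAP does not state either explicitly.

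The count part is a mismatch between periods. It does not show that consecutive-day merging is wrong for the IVMP.

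On the assumed arm of 16 with one affected participant, mean total dose is about 2% too high in the first case, and mean interval differs by 0.04 weeks (1.1%) in the second. The documents do not say how many participants had such infusions, so the actual effect may be zero. Participants without them are unaffected. Individual IVMP infusions are listed (Listing 16.2.4.5), so the cases can be found.

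**What to change.** In section 6.3.2.5:

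1. Sum IVMP total dose over single (merged) administrations, as section 6.5.1.1 does for the DBTP.
2. Give each merged administration one dose: the course dose once, or the sum of the daily doses if records are daily. State which of these the record holds.
3. Use the DBTP merging rule for the IVMP count: infusions under the same visit number, or unscheduled infusions at most 5 days from first to last, are one administration.
4. Re-derive Table 14.1.13.

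The first two changes close the dose gap. The third makes the two intervals rest on the same count. The DBTP text needs no change. The cost is a few sentences and one descriptive table from data already collected. The downside is that IVMP figures already shown at an interim analysis may change slightly for participants with unscheduled infusions, which a footnote can explain.
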